Subjects who discontinue the double-blind study treatment and enter open-label treatment with CZP will be assessed 2 and 4 weeks after open-label CZP treatment has been initiated and every 12 weeks thereafter. Alternatively, subjects who discontinue the double-blind study treatment and receive other treatment (including biologics) will be assessed every 12 weeks after initiation of the open-label other treatment (OL-OT). In either alternative schedule, assessments should be conducted until as close as possible to Week 52 (within  $\pm 4$  weeks), where Week 52 is relative to

the original randomization at Week 0. Subjects will then be invited to the Week 52 assessment visit.

**Period 3** (Follow-up period) - All subjects not participating in the SFE period after Week 52, including those withdrawn from the study prematurely, will have a single Follow-up visit, 8 weeks after Week 52/WD visit (10 weeks after their last administration of study medication).

**SFE Period** - Week 52 to Week 156, open-label:

At the completion of the Week 52 visit assessment, subjects on double-blind study treatment may receive open-label CZP treatment for an additional 2 years. Subjects who withdrew from double-blind study treatment and transitioned to open-label CZP treatment are also eligible to participate in the SFE period after completing the Week 52 visit assessment. Subjects on OL-OT are not eligible to participate in the SFE period.

Eligible subjects are allowed to roll-over to the SFE-period up to 3 months after completion of the Week 52 assessments.

Starting at Week 64, all subjects are to visit the site approximately every 12 weeks ( $\pm 2$  weeks) for assessments. The last dosing visits will be at Week 154. The final study assessments are performed at Week 156/Safety Follow-up Extension-Early Withdrawal Visit (SFE-WD) ( $\pm 1$  week). However a  $\pm 4$  week window will be used in the analysis for the Week 156 timepoint. The expected day for Week 156 will be calculated assuming that the SFE period start was on Week 52, i.e. Week 156 will be expected to be  $(156-52) \times 7$  days after Week 52. For patients where the first dose after the Week 50 visit is before the SFE informed consent the width of the lower boundary of the Week 156 window will be increased further by the absolute number of days between the first dose after the Week 50 visit and the SFE informed consent date.

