### **2.3.2 Study duration per subject**

For each subject, the first 3 periods of the study will last a maximum of 66 weeks, as follows:

- Up to 6 weeks in the Screening period
- 52 weeks in the double-blind period
- A Follow-up visit, 8 weeks after Week 52/WD visit for subjects not participating in the SFE Period.

For subjects participating in the SFE period, the study will extend up to a maximum of 104 additional weeks.

The end of the study will be defined as the date of the last subject's last visit, defined as the Follow-up Visit 8 weeks after Week 52/WD visit for subjects not participating in the SFE Period, or the last visit of the SFE Period (Week 156/SFE-WD).

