#### **3.2.1.6 SFE period**

The SFE period starts when the subject takes their first dose of OL-CZP that is after week 50 and after date of informed consent for the SFE. Visit based efficacy or safety data that is recorded on the day of the first SFE period dose will be assigned to the previous period unless available time information clearly indicates that it was recorded after the first administration of SFE period treatment. There are some subjects who took their first dose of OL-CZP that is after week 50

before the informed consent for the SFE. In such cases the SFE period will be programmed to start at the informed consent date.

The SFE period ends when the subject discontinues from or completes the study following SFE enrollment (Week 156/SFE-WD).

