### **4.3 Interim analyses and data monitoring**

An interim analysis is planned after the completion of the double-blind period of the last subject at Week 52. The timing of the analysis will be when the last subject completes Week 52 visit in accordance with the double-blind, OL-CZP or OL-OT schedule. At this time, all visit based data from the double-blind period up to and including Week 52 visit, all open-label visit based data up to Week 52 visit, all available Follow-up data for subjects already completing the study, all hospitalization/emergency room visit and health care provider consultation data, all study medication discontinuation and all prior and concomitant medication data including concomitant medical procedures, will be locked. Subjects still on the study awaiting Follow-up visit or in SFE, will continue to have AEs, laboratory, vital sign, PK and physical examination data collected per schedule until completion of the Follow-up or SFE period, at which point they will complete the study termination eCRF page. At the time of the interim analysis Week 52 DB lock, adverse event data entered to date will be cleaned but not locked. This will allow ongoing adverse event entry during the Follow-up and SFE periods. The treatment codes will be made available to the study reporting team and an interim study report will be written. All tables, listings and figures described in this SAP for analysis of the double-blind 52-week treatment period will be produced at the time of the Week 52 DB lock. The Investigators and subjects will remain blind to the assigned CZP dose regimen of the double-blind period.

After the last subject has completed the SFE period, the database will be fully locked, and a final study report will be written. For subjects in the SFE period, from the Week 52 visit onward, subjects will be treated with OL-CZP until Week 156/SFE-WD visit. During this time, only adverse events, concomitant medication related to adverse events, and study drug dispensation information will be collected. Efficacy assessments and study termination data will be collected at Week 156/SFE-WD as described in Table 5-6 of the study protocol. Therefore, at the final DB lock, the following tables and listings will be produced.

- Table 1.1.2: Disposition of Subjects Screened
- Table 1.2.1: Disposition and Discontinuation Reasons
- Table 1.2.2: Number of Subjects Completing each Visit
- Table 1.3: Disposition of Analysis Sets

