Exposure to the OL-CZP treatment will also be calculated using the above 4 methods considering only dosing during the time the subject is receiving OL-CZP study medication prior to Start of SFE. Exposure during the SFE period will be calculated using methods 2, 3 and 4 assuming first dose in the SFE period starts when the subject takes their loading dose/first dose of OL-CZP in the SFE period and ends when the subject has their last administration of study medication (or if missing, the date of withdrawal from the SFE). Total CZP incl DB and OL

exposure will be calculated using all 4 methods, by summing the exposure to CZP during the double-blind and OL- CZP periods. Total CZP incl DB, OL, and SFE OL will be calculated using methods 2, 3 and 4, by summing the exposure to CZP during the double-blind, OL-CZP and SFE periods. Note that for Total CZP incl DB, OL, and SFE OL method 1 will not be calculated as the SFE period does not collect data on dose administration. Exposure to OL-OT will not be calculated.

For the first 3 approaches, tables will summarize exposure for the placebo, CZP 200mg Q2W, OL-CZP treatment groups (split by the treatment taken during the double-blind period), SFE OL-CZP, Total CZP incl DB and OL and Total CZP incl DB, OL, and SFE OL (for methods 2 and 3 only).

The following doses will be presented in a listing:

- very first dose in the study, the very last dose in the study and the difference between them
- last dose in the DB period (i.e. last DB dose or last OL dose), the last SFE dose and the difference between them.

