**Table 11–1: Assignment of Adverse Events to Study Periods**

Type of Subject	Assignment Rule Based on AE Start Date	Assignment
Subjects who enter the open-label period	
1. Start date is on or after first study drug administration during the double-blind period and on or before the last study drug administration in the double-blind period + 70 days and before the start date and time of OL-CZP or OL-OT.
 
Note: If a subject continues in the study with OL-OT visits but without taking any relevant other medication, there will be no start date of the other treatment period and all AEs with a start date within 70 days after last administration will be assigned to the DB period.
	Double-blind TEAE
	
2. Start date is on or after the start date of OL-CZP and on or before the last study drug administration in the OL-CZP period + 70 days and
 
 
• before the start date of OL-OT (for subjects moving into OL-OT), or
 
• before the SFE period start (for subjects moving into SFE period)
 
	Open-label CZP TEAE
	
3. Start date is on or after the start date of OL-OT.
 
Note: Other treatment adverse events will not be summarized, but only presented in listings
	Open-label other treatment TEAE
Subjects who enter the pre-SFE period	Start date is after the last double-blind or OL-CZP dose + 70 days and is before the SFE period start.	Pre-SFE AE
Subjects who enter the open-label SFE period	Start date is on or after the SFE period start and on or before the SFE period end + 70 days.	SFE TEAE

If AE intensity or relationship is missing, then the given event will be imputed as severe or related, respectively.

The frequency of all AEs including TEAEs will be presented for each treatment group separately by System Organ Class, high level term, and preferred term. The data will be displayed as number of subjects experiencing the AEs, percentage of subjects, and number of AEs. Certain summaries will also include exposure-adjusted incidence rates and event rates. TEAEs will be summarized by treatment and period as described in [Section 3.6](#).

The following AE summaries will be presented:

- Overview of TEAE
- Overview of Pre-SFE AEs

- TEAE
- Serious TEAE
- Non-serious TEAE
- TEAE with fatal outcome
- TEAE leading to permanent withdrawal of study medication
- Severe TEAE (included in TEAE table by intensity)
- Drug-related TEAE (included in TEAE table by relationship)

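### Method 3 exposure runs 70 days past the last dose even where follow-up has stopped or the next treatment period has begun, so the event rates based on it are too low (about 7% to 9% for an SFE completer)

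*SAP*

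**What the plan says.** **Observation.** Section 2.3.1 states "The last dosing visits will be at Week 154", with final assessments at Week 156/SFE-WD. The visit that covers the washout is kept for others: "All subjects not participating in the SFE period after Week 52, including those withdrawn from the study prematurely, will have a single Follow-up visit". Section 2.3.2 repeats this: "A Follow-up visit, 8 weeks after Week 52/WD visit for subjects not participating in the SFE Period". Under Section 4.3, adverse event and other data for subjects awaiting Follow-up or in the SFE are "collected per schedule until completion of the Follow-up or SFE period, at which point they will complete the study termination eCRF page".

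**Event window.** The SFE row of Table 11-1 is "Start date is on or after the SFE period start and on or before the SFE period end + 70 days". Section 3.2.1.6 defines that end: "The SFE period ends when the subject discontinues from or completes the study following SFE enrollment (Week 156/SFE-WD". The other rows of Table 11-1 that carry a 70-day tail tie it to the last dose. Table 11-1 also stops double-blind events when OL-CZP, OL-OT or the SFE begins, and stops OL-CZP events when OL-OT or the SFE begins.

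**Exposure.** Section 11.1 says: "Exposure during the SFE period will be calculated using methods 2, 3 and 4". Method 3 adds 70 days after the last injection. Its only reductions are for death and for drug holidays longer than 70 days. Method 2 adds 14 days, and method 4 is essentially method 2 censored at the first occurrence of the event. SFE exposure is anchored on the last administration, or on the SFE withdrawal date if that is missing. The same section notes that dose administration is not recorded in the SFE. Total CZP exposure is the sum of the period exposures. No stop at the start of the next period is written for method 3.

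**Rates.** Section 11.2 adjusts rates with methods 3 and 4. The EAIR uses exposure censored at the event; the EAER uses all events over the whole exposure.

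**The concern.** An exposure-adjusted rate is interpretable only if events could be recorded throughout the time in its denominator. In the SFE, observation ends at Week 156/SFE-WD, method 3 exposure ends at Week 164 for a completer, and the event window ends at Week 166. At the change from double-blind to SFE treatment, events move to the new period while the old period's exposure keeps running. In both places method 3 adds time that cannot yield an event for that column, and the rate falls for that reason alone.

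The rates at stake are the EAERs planned for all TEAEs, serious TEAEs, TEAEs leading to withdrawal of study medication and several events of special interest, in the SFE column and in the CZP total that includes it. Long-term safety is the purpose of this extension.

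**Working it through.** **The plan's own figure.** The Follow-up visit for subjects outside the SFE is "8 weeks after Week 52/WD visit (10 weeks after their last administration of study medication"). Last double-blind dose at Week 50 = day 350; 350 + 70 = 420 = Week 60; Week 52 + 8 weeks = Week 60. The figures agree. A double-blind completer who does not enter the SFE has all 420 method 3 days covered by a visit.

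**SFE completer.** Inputs: SFE start taken as Week 52, last dose Week 154, last visit Week 156 (Section 2.3.1); tails of 70 and 14 days (Section 11.1). Observed time = (156 − 52) × 7 = 728 days. Time to last dose = (154 − 52) × 7 = 714 days. Unobserved share = (counted − observed) / counted.

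| Exposure rule | Counted days | Unobserved | Share |
|---|---|---|---|
| Method 3, last dose known | 714 + 70 = 784 | 56 | 7.1% |
| Method 3, withdrawal date used instead | 728 + 70 = 798 | 70 | 8.8% |
| Method 4 before censoring, last dose known | 714 + 14 = 728 | 0 | 0% |
| Method 4 before censoring, withdrawal date used instead | 728 + 14 = 742 | 14 | 1.9% |

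With a constant event rate and nothing captured after the last visit, the rate shrinks by the share shown. An illustrative true EAER of 200 per 100 subject-years would be reported as 200 × 728 / 784 = 186.

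**Early SFE withdrawal, method 3.** The SAP does not fix the gap between the last dose and the SFE-WD visit, so assume 14 to 0 days; 56 to 70 days are then unobserved.
- Last dose 24 weeks after SFE start: 168 + 70 = 238 days; 56/238 to 70/238 = 23.5% to 29.4%.
- Last dose 52 weeks after SFE start: 364 + 70 = 434 days; 56/434 to 70/434 = 12.9% to 16.1%.

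These are shares for single subjects. The rate divides by summed exposure. If, say, 20% withdrew at SFE week 52 with a last dose at week 50 (350 + 70 = 420 days each), mean counted time would be 0.8 × 784 + 0.2 × 420 = 711 days and the pooled loss 56/711 = 7.9%.

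**Double-blind period, direct rollover.** Method 3 as written counts 350 + 70 = 420 days, but Table 11-1 stops double-blind events at SFE start. With SFE start at Week 52 (day 364), 420 − 364 = 56 days, or 56/420 = 13.3%, cannot hold a double-blind TEAE. The loss is 10.0% with SFE start on day 378, 6.7% on day 392, and zero from day 420 (Week 60).

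**Total including the SFE.** A subject randomized to CZP who rolls over at Week 52 and completes contributes 420 + 784 = 1204 days. Time from first dose to Week 156 is 156 × 7 = 1092 days. The excess is 112 days (112/1204 = 9.3%): 56 counted twice around SFE start and 56 after the last visit.

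**Event window.** For a completer it ends 14 + 70 = 84 days after the Week 154 dose, against exposure tails of 70 days (method 3) and 14 days (method 4).

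**The case against.** The strongest reply is that the absence of a visit does not prove that no event is recorded. Reporting after the last visit is a protocol matter and the protocol is not at hand. A window running past Week 156 could have been written to catch late reports. This stands as a limit on certainty. But Section 4.3 describes collection only until the SFE is completed, and nothing in the SAP provides active follow-up comparable to the Week 60 visit.

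It is also fair that the EAIR, the rate that carries the confidence interval, is almost untouched when computed on method 4; that the SFE rate is a descriptive single-arm figure with no test attached; and that the large early-withdrawal shares come from subjects who contribute little person-time. All of this stands and keeps the point modest.

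The SFE row of Table 11-1 does not itself dilute anything. It classifies events. If nothing is reported late, it changes no count; if something is, it keeps that event in the TEAE tables. Shortening it to study termination would make such events non-treatment-emergent.

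A reader might infer that SFE rates will look lower than double-blind rates by construction. The SAP does not support that. It is so against subjects with a Follow-up visit (no loss), but direct rollovers at Week 52 lose 13.3% in the double-blind period as written, against 7.1% in the SFE. The direction depends on the mix of subjects and on whether double-blind exposure is cut at SFE start. A reader might also infer that exposure runs 70 days past the end of the SFE. It runs 56 days past Week 156, and reaches 70 only when the withdrawal date stands in for a missing dose date.

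**Conclusion.** The point holds for rates that use method 3. For an SFE completer the denominator contains 7.1% unobserved time, or 8.8% under the missing-date rule, which may apply often because dose administration is not recorded in the SFE. The share is larger for early withdrawers. In the total including the SFE, a CZP subject rolling over directly at Week 52 carries 9.3% excess exposure.

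This rests on four assumptions: the EAER is computed on method 3 (the natural reading, since method 4 is the censored one, though Section 11.2 does not assign them outright); the event rate is constant; no event is captured after Week 156/SFE-WD; and roll-over occurs at Week 52 for the double-blind and total figures. The EAIR on method 4 is not materially affected, and no comparison of SFE with double-blind rates is claimed. It is a moderate bias in descriptive safety rates and worth removing because the correction is simple.

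**What to change.** In Section 11.1:
- End SFE method 3 exposure at the earliest of last SFE dose + 70 days, study termination (Week 156/SFE-WD) and death. A completer then counts 728 days whether or not the last dose date is known.
- End double-blind and OL-CZP method 3 exposure at the start of the next treatment period (OL-CZP, OL-OT or SFE), matching the stops Table 11-1 already applies to events. The direct rollover then totals 364 + 728 = 1092 days.

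In Table 11-1, reconcile the SFE row's period-end anchor with the last-dose + 70 days anchor used in the other rows, but do not truncate the TEAE window at study termination.

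The cost is a few lines of SAP text and a minimum in each exposure derivation. No new data are needed. The downside for the sponsor is that SFE EAERs become slightly less favourable.

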- Serious TEAE by relationship
- Non-serious TEAE by relationship
- Fatal TEAE by relationship
- TEAE of special interest (see below)
- TEAE sorted by incidence of PTs in the CZP 200mg group (SOC and higher level term [HLT] will not be utilized)
- Non-serious TEAE with an incidence of more than 5% in 1 of the 2 randomized groups (HLT will not be utilized)
- Non-serious TEAE with an incidence of more than 5% in 1 of the 2 randomized groups by relationship (HLT will not be utilized)
- TEAE subject numbers
- TEAEs with a CZP incidence  $\geq 1\%$  and CZP incidence  $>$  PBO incidence

The AEs of interest and the approach for summarizing them is briefly described below. Further information is provided in the guidance document (AEs of Interest – Cimzia Program 2018-01-05).

1. Serious infections, including opportunistic infections. Serious infections will be summarized using the Serious TEAE table. No separate table is planned. In addition, opportunistic infections (including tuberculosis) will be presented in a table using UCB-defined search criteria.
2. Malignancies, including lymphoma. These will be presented in 2 tables using the Standardized MedDRA Query (SMQ) criteria “Malignant or unspecified tumours” and “Malignant tumours” respectively.
3. Serious cardiovascular events (also called major adverse cardiac events or MACE). These will be presented in a table including all serious TEAEs with the SMQs of “Haemorrhagic central nervous system vascular conditions”, “Conditions associated with central nervous system haemorrhages and cerebrovascular accidents”, and “Ischaemic central nervous system vascular conditions” with the exception of events coding to a PT of “Transient ischaemic attack”, including all serious TEAEs with the HLT of “Ischaemic coronary artery disorders” except events coding to PTs of “Chest Pain” or “Chest discomfort” and including all serious

TEAEs with HLTs of “Heart Failures NEC”, “Left Ventricular Failures”, or “Right Ventricular Failures” and which also code to the SOC of “Cardiac Disorders”.

4. Congestive heart failure. These will be manually identified by the study physician from the TEAE table. No separate table is planned.

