5. Demyelinating-like disorders will be presented in table which is based on the SMQ = “Demyelination”. The SMQ search should include all TEAEs which code to a PT included in Scope=Narrow group within the SMQ. TEAEs which code to a PT included in the Scope=Broad group within the SMQ should be excluded from the search.
6. Aplastic anemia, pancytopenia, thrombocytopenia, neutropenia, and leucopenia. These will be presented in a table using the criteria SMQ = “Haematopoietic cytopenias” in the subset of Serious TEAEs.
7. Serious bleeding events. These will be presented in a table using the criteria SMQ = “Haemorrhage terms (excl laboratory terms)” in the subset of Serious TEAEs.
8. Lupus and lupus-like illness. These will be manually identified by the study physician from the TEAE table. No separate table is planned.
9. Serious skin reactions (eg, Stevens-Johnson Syndrome, toxic epidermal necrosis, and erythema multiforme). These will be manually identified by the study physician from Serious TEAE table. No separate table is planned.

The tables for 1, 2, 3, 5, and 6 above, will include the exposure-adjusted incidence rate (EAIR) with associated 95% CI, and the exposure-adjusted event rate (EAER) as described below.

Although not officially AEs of interest, the following events will also be summarized as described in the AEs of Interest – Cimzia Program 2018-01-05 guidance document.

1. Hepatic events. These will consist of a subset of all TEAEs, identified using the following 5 SMQs: Cholestasis and jaundice of hepatic origin; Hepatic failure, fibrosis, and cirrhosis and other liver damage-related conditions; Hepatitis, noninfectious; Liver-related investigations, signs and symptoms; and Liver-related coagulation and bleeding disturbances.
2. Hypersensitivity reactions and anaphylactic reactions. Hypersensitivity reactions will be summarized as any TEAEs occurring on the same day or the day after injection was received, which code to the following preferred terms: Administration site hypersensitivity, Documented hypersensitivity to administered product, Drug hypersensitivity, Hypersensitivity, Hypersensitivity vasculitis, Infusion site hypersensitivity, Injection site hypersensitivity, Medical device site, hypersensitivity, Type II hypersensitivity or Type IV hypersensitivity reaction. Anaphylactic reactions will be defined using an algorithmic approach as described in the “AEs of Interest – Cimzia Program 2018-01-05” guidance document.

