- TEAE leading to permanent withdrawal of study medication
- Severe TEAE (included in TEAE table by intensity)
- Drug-related TEAE (included in TEAE table by relationship)
- Serious TEAE by relationship

- Non-serious TEAE by relationship
- Fatal TEAE by relationship
- Injection reactions (Injection site reactions, systemic injection reactions, acute systemic injection reactions, and delayed systemic injection reactions)
- TEAE of special interest (see below)
- TEAE sorted by incidence of PTs in the CZP 200mg group (SOC and higher level term [HLT] will not be utilized)
- Non-serious TEAE with an incidence of at least 5% in 1 of the 2 randomized groups (HLT will not be utilized)
- Non-serious TEAE with an incidence of at least 5% in 1 of the 2 randomized groups by relationship (HLT will not be utilized)
- TEAE subject numbers

The AEs of interest and the approach for summarizing them is briefly described below. Further information is provided in the guidance document (AEs of Interest – Cimzia Program 9February2017).

11. Serious infections, including opportunistic infections. Serious infections will be summarized using the Serious TEAE table. No separate table is planned. In addition, opportunistic infections (including tuberculosis) will be presented in a table using UCB-defined search criteria.
12. Malignancies, including lymphoma. These will be presented in 2 tables using the Standardized MedDRA Query (SMQ) criteria “Malignant or unspecified tumours” and “Malignant tumours” respectively.
13. Serious cardiovascular events. These will be presented in a table including all serious TEAEs with the SMQs of “Haemorrhagic central nervous system vascular conditions” and “Ischaemic central nervous system vascular conditions”, including all serious TEAEs with the HLT of “Ischaemic coronary artery disorders” except events coding to PTs of “Chest Pain” or “Chest discomfort” and including all serious TEAEs with HLTs of “Heart Failures NEC”, “Left Ventricular Failures”, or “Right Ventricular Failures” and which also code to the SOC of “Cardiac Disorders”.
14. Congestive heart failure. These will be manually identified by the study physician from the TEAE table. No separate table is planned.
15. Demyelinating-like disorders. These will be manually identified by the study physician from the previously described TEAE table. No separate table is planned.

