#### **Change #4**

Section 2.2.4.1 and 11.2: Summaries of the following were updated:

- Injection reaction summaries were removed.
- TEAEs with CZP incidence  $\geq 1\%$  and CZP incidence > PBO incidence was added.
- Serious Cardiovascular and demyelinating-like disorder were updated to align to latest UCB standards.
- The following was changed to be optional: TEAEs reported after: new biologic, changing NSAID, changing DMARD or addition of oral corticosteroid.

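### Congestive heart failure, lupus-like illness and serious skin reactions are identified manually from tables laid out by treatment group, with no category count or rate planned; a coded rule is at hand for heart failure

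*SAP*

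**What the plan says.** Section 2.2.4.1.1 lists nine adverse events of special interest, each as a yes/no presence variable under the secondary safety variables. Section 11.2 then says how each is summarised. Three are handled by hand:

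- Item 4: "Congestive heart failure. These will be manually identified by the study physician from the TEAE table. No separate table is planned".
- Item 8: "Lupus and lupus-like illness. These will be manually identified by the study physician from the TEAE table. No separate table is planned".
- Item 9, serious skin reactions, with three example diagnoses: "These will be manually identified by the study physician from Serious TEAE table. No separate table is planned".

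Section 11.2 also says that adverse event frequencies are shown separately for each treatment group, by SOC, HLT and PT. On rates it says: "The tables for 1, 2, 3, 5, and 6 above, will include the exposure-adjusted incidence rate (EAIR) with associated 95% CI". Items 4, 8 and 9 are not in that list.

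Section 11.2 describes its account of these events as brief and refers to a sponsor guidance document on adverse events of interest for more. That document is not part of the SAP.

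**The concern.** A yes/no safety variable should come from a stated rule that gives the same answer whichever arm the subject is in. For these three the SAP's instruction is manual identification from a table whose columns are the treatment groups. The SAP states no term list for a programmer to apply, and it plans no output showing how many subjects per arm had the category.

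What is at stake is modest. These are named harms for which a reader will look for a category total by arm. Without one, the reader must assemble it from individual coded terms and cannot check the selection against a rule.

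**Working it through.** The plan gives no figure on this point, so the check is a comparison of its own provisions.

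**Step 1. The nine items as Section 11.2 treats them.**

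| Item | Rule stated in the SAP | Own table | In the EAIR/EAER list |
|---|---|---|---|
| 1 Serious infections | Main Serious TEAE table; opportunistic infections by sponsor-defined search | Opportunistic infections only | Yes |
| 2 Malignancies | Two SMQs | Yes | Yes |
| 3 Serious cardiovascular events | SMQs and HLTs, serious events only | Yes | Yes |
| 4 Congestive heart failure | Manual | No | No |
| 5 Demyelinating-like disorders | One SMQ, narrow scope | Yes | Yes |
| 6 Cytopenias | One SMQ, serious events only | Yes | Yes |
| 7 Serious bleeding | One SMQ, serious events only | Yes | No |
| 8 Lupus-like illness | Manual | No | No |
| 9 Serious skin reactions | Manual, serious events only, three examples | No | No |

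Manual identification applies to 3 of 9 items. Items 2, 3, 5, 6 and 7 have a coded rule written into the SAP.

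**Step 2. Events of lower standing are specified more tightly.** Section 11.2 goes on: "Although not officially AEs of interest, the following events will also be summarized as described in the AEs of Interest". Hepatic events then get five SMQs, and hypersensitivity reactions get a PT list.

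**Step 3. A heart-failure rule already exists.** Item 3 captures serious heart failure through three HLTs (the NEC, left ventricular and right ventricular failure terms), restricted to the Cardiac Disorders SOC. It covers serious events only and pools them with cerebrovascular and ischaemic coronary events, so it gives no heart-failure count. Without the seriousness filter, the same HLTs would supply item 4.

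**Step 4. The same change has been made before.** This is history only, not an error in the current text. Under Amendment 2 the SAP read: "Demyelinating-like disorders. These will be manually identified by the study physician from the previously described TEAE table. No separate table is planned". Amendment 3 reports: "Serious Cardiovascular and demyelinating-like disorder were updated to align to latest UCB standards". Item 5 now says: "The SMQ search should include all TEAEs which code to a PT included in Scope=Narrow group within the SMQ".

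**Step 5. What a reader can still recover.**

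- *Events.* All of them. Section 11.2 plans rows by SOC, HLT and PT for each arm, a summary of TEAE subject numbers, and listings of TEAEs and serious TEAEs. Section 3.1 adds by-subject listings of all data.
- *Distinct subjects in a category.* Recoverable from the listings. Adding the printed rows is not enough, because a subject with two qualifying terms appears in both.
- *A category EAIR.* Not obtainable by adding printed rates. Method 4 in Section 11.1 censors exposure separately for each PT, so exposure would have to be recalculated to the first event in the category.

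**Step 6. What the SAP leaves open.** Section 4.3 releases treatment codes to the study reporting team at the Week 52 lock. It does not say whether the study physician belongs to that team. Section 11.2 does not say when the manual identification takes place.

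**The case against.** The strongest reply is that nothing is lost. Every event appears by arm at HLT and PT level, and the TEAE and Serious TEAE summaries carry EAIR with exact 95% CIs and EAER. The heart-failure HLTs are already rows in those tables, and serious heart failure is also inside item 3. This stands, and it limits the point to a missing category summary and an unstated rule.

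Second, the SAP openly abridges a guidance document. It relies on that document for the anaphylaxis algorithm, so term lists for these three may sit there too. This also stands: for lupus-like illness and skin reactions the remedy depends on what that document holds. Even so, the SAP's operative instruction is manual identification with no table.

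Third, item 1 also says that no separate table is planned for serious infections, so reading from the main tables is this plan's normal format. That is only partly an answer. Item 1 says the Serious TEAE table is itself the summary, and no one is asked to select cases from it.

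A reader might infer that the selection is made unblinded, or that it is biased towards an arm. The documents do not support this. A table laid out by arm shows what the physician reads from, not whether the treatment labels are visible or when the reading is done. A reader might also infer that events could go unreported, and the planned tables and listings rule that out.

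**Conclusion.** The point holds as a small improvement in descriptive safety reporting. Three of nine secondary presence variables rest on manual identification from tables arranged by treatment group, with no planned category count or rate. It is firm for congestive heart failure, because the SAP already contains a suitable coded rule. It is conditional for lupus-like illness and serious skin reactions, because the guidance document may already define them.

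No hypothesis test or efficacy result is touched. The SAP gives no expected event numbers for these categories, so the effect on any reported figure cannot be sized from the document. The conclusion assumes that the physician's blinding and the timing of the review are not fixed elsewhere, for example in the guidance document.

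**What to change.** - **Congestive heart failure.** Replace manual identification with item 3's three heart-failure HLTs, restricted to the Cardiac Disorders SOC and applied to all TEAEs. At final lock, tabulate the category by arm and period with each subject counted once. Add EAIR with its 95% CI, with exposure censored at the first event in the category, and EAER.
- **Lupus-like illness and serious skin reactions.** If the guidance document has a term list, use it and name it in the SAP. If not, have the manual selection made on coded terms without treatment columns, and report the count by arm.
- **All three.** State that the rule was added after the Week 52 outputs, and keep the physician's review as narrative.

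The cost is SAP wording and up to three small tables from coded data. Section 4.3 leaves adverse event data unlocked at Week 52 and already plans adverse event tables at final lock. There are two drawbacks. A coded rule may capture a few irrelevant terms, which the narrative can explain. The rule would also be set after the Week 52 unblinding, which is why it should be disclosed and, for heart failure, taken unchanged from terms already in the SAP.
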